#### **Intent-to-Treat (ITT) Population:**

All randomized subjects regardless of actual treatment and subsequent withdrawal from the study or deviation from the protocol. At least one observation should be recorded.

### **14.4. Level of Statistical Significance**

All planned analysis for this study will be conducted with an overall type I error rate of 5%. The study hypotheses will be tested using the following gatekeeping strategy; If the primary hypothesis is met, then the secondary hypotheses will be tested. If the primary and secondary hypotheses are met, all tertiary hypotheses will be evaluated for both between the study arms and within the second arm. If the primary and secondary hypotheses regarding CLUE comfort are met, then the tertiary hypotheses relevant to this endpoint will be evaluated for both between the study arms and within the second arm. If only the primary hypothesis for CLUE comfort is met then, then associated tertiary hypotheses relevant to this endpoint will only be evaluated between study arms. If both secondary hypotheses regarding CLDEQ8-Scores are met, then the tertiary hypotheses relevant to this endpoint will be evaluated for between the study arms only and within the second arm. If only 1 of the secondary hypotheses regarding CLDEQ8-scores is met, then the associated tertiary hypotheses relevant to this endpoint will be evaluated between study arms.

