### **2.3. Hypotheses**

Primary Hypothesis:

The Primary hypothesis will be evaluated between the two study arms; only the first period will be considered for the second study arm.

| Primary Hypotheses |   |
|--------------------|---|
| Endpoint           | Hypothesis  |
| CLUE Comfort       | The Test lens will be non-inferior to the Habitual lens with respect to the change in CLUE comfort score from baseline at 2-week follow-up. A non-inferiority margin of -5 points on the CLUE scale will be used. |

Secondary Hypotheses:

The primary hypothesis must be met in order to test the secondary hypotheses. The secondary hypothesis regarding the change in CLDEQ-8 Scores will be evaluated between the two study arms; only the first period will be considered for the second study arm. The remaining two secondary hypotheses will be evaluated within the second study arm only.

| Secondary Hypotheses          |  |
|-------------------------------|--|
| Endpoint                      | Hypothesis   |
| Change in CLDEQ-8 Total Score | The Test lens will be non-inferior to the Habitual lens with respect to the change in CLDEQ-8 total score from baseline at 2-week follow-up. A non-inferiority margin of 3 points on the CLDEQ-8 scale will be used. |
| CLDEQ-8 Total Score           | The Test lens will be non-inferior to the Habitual lens with respect to CLDEQ-8 total score at 2-week follow-up. A non-inferiority margin of 3 CLDEQ-8 points will be used.  |
| CLUE Comfort                  | The Test lens will be non-inferior to the Habitual lens with respect to CLUE comfort score at 2-week follow-up. A non-inferiority margin of -5 CLUE points will be used.   |

The primary hypothesis must be met in order to satisfy the objective of the study.

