Table 9 displays the sample size estimates for the primary endpoint of CLUE Comfort score, and the secondary endpoint of CLDEQ8- Scores for different scenarios of effect sizes. CLDEQ-8 power analysis was provided for informational purposes. All Sample size calculations were performed with 80% power and 2-sided alpha=0.05. With respect to CLDEQ-8 Scores, for ARM1 a standard deviation of 7.17 was utilized (See Table 7 ), while a standard deviation of 5.0 was utilized for ARM2 in each calculation for the various effect sizes. The different effect sizes for CLDEQ-8 scores were based on the historical effect sizes provided in Table 7. Historically, on average AO1D improved CLEQ8-scores about 7 points after 2-weeks of wear. The power analysis for CLDEQ8-scores is displayed in Table 9 below. With respect to CLUE comfort scores, for ARM1 a standard deviation of 25.21 was used (See Table 8) while, a standard deviation of 18.12 was utilized for ARM2 in the calculation for each scenario. Due to the varying effect sizes displayed in Table 8 above, effect sizes of 3, 5 and 9 were utilized as a more conservative estimate for the sample size calculation since there was a high a difference observed between AO1D and subjects' habitual lenses with respect to CLUE Comfort (22.6 points) in ██████.

Sample size and power calculations for each endpoint and scenario were calculated using a 2-sided Satterthwaite t-test assuming unequal variances using the POWER^11 procedure in SAS Version 9.4.

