### **Hypothesis Testing:**

The null and alternative hypotheses for non-inferiority of the Test relative to Control are as follows:

$$H_0: \Delta \leq -5$$

$$H_A: \Delta > -5,$$

where  $\Delta$  is the difference between lens types (Test minus Control) in mean change from baseline at 2-week follow-up. Non-inferiority of the Test lens relative to the Control lens will be based on the LSM difference in the score change from baseline at 2-week follow-up and its corresponding 95% confidence interval from the final model. The lower bound of the 95% CI will be compared to the non-inferiority margin of -5. If the lower bound is greater than -5, the null hypothesis will be rejected, and the Test lens will be considered non-inferior to the Control lens. If non-inferiority of the Test lens over Control lens is met, then superiority test will be also conducted on the ITT population. If the lower bound is greater than 0, then the superiority of the Test lens over the Control lens will be established

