# Clinical Study Protocol

## Johnson & Johnson Vision Care, Inc.

### **Hypothesis Testing:**

The null and alternative hypotheses for non-inferiority of the Test relative to Control are as follows:

$$H_0: \Delta \geq 3$$

$$H_A: \Delta < 3,$$

where  $\Delta$  is the difference between lens types (Test minus habitual lens) in mean change from baseline at 2-week follow-up. Non-inferiority of the Test lens relative to the Control lens will be based on the least square mean (LS Mean) difference in the score change from baseline at 2-week follow-up and its corresponding 95% confidence interval (CI) from the final model. The upper bound of the 95% CI will be compared to the non-inferiority margin of 3. If the upper bound is less than 3, the null hypothesis will be rejected, and the Test lens will be considered non-inferior to the Control lens. If non-inferiority of the Test lens over Control lens is met, then superiority test will be also conducted on the ITT population. If the upper bound is less than 0, then the superiority of the Test lens over the Control lens will be established.

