### **Hypothesis Testing:**

The null and alternative hypotheses for non-inferiority of the Test relative to Control are as follows:

$$H_0: \Delta \geq 3$$

$$H_A: \Delta < 3,$$

where  $\Delta$  is the difference between lens types at 2-week follow-up (Test (AO1D) minus Control (Habitual Lenses)). Non-inferiority of the Test lens relative to the Control lens will be teste using a 2-sided 95% CI constructed for the LSM difference at 2-week follow-up Non-inferiority will be established if the upper bound of the 95% CI is below 3 CLDEQ-8 points. If non-inferiority of the Test lens over Control lens is met, then superiority test will be also conducted on the ITT population. If the upper bound is less than 0, then the superiority of the Test lens over the Control lens will be established.

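### The tertiary gate is stated in conflicting ways, and the 5% overall type I error in section 14.4 is not guaranteed for the secondary hypotheses or provided for the tertiary items.

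*Combined protocol and SAP*

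**What the plan says.** - **Stated error rate.** Section 14.4: "All planned analysis for this study will be conducted with an overall type I error rate of 5"%. It does not say whether this is one- or two-sided. Section 14.2 says "All Sample size calculations were performed with 80% power and 2-sided alpha=0.05".
- **First gate.** Section 2.3: "The primary hypothesis must be met in order to test the secondary hypotheses". No order or alpha split among the three secondaries appears in 2.3, 14.4 or 14.6.
- **Secondary tests.** For change in CLDEQ-8 between arms, section 14.6 says "The upper bound of the 95% CI will be compared to the non-inferiority margin of 3". For the other two, section 2.3 says "The remaining two secondary hypotheses will be evaluated within the second study arm only". The within-arm CLDEQ-8 rule is "Non-inferiority will be established if the upper bound of the 95% CI is below 3 CLDEQ-8 points", and the within-arm CLUE rule compares the lower 95% bound with -5.
- **Superiority.** Section 14.5, after the primary: "If non-inferiority of the Test lens over Control lens is met, then superiority test will be also conducted on the ITT population". Section 14.6 repeats this after each secondary.
- **Tertiary tests.** Section 14.7 judges 28 individual items (4 CLDEQ-8, 8 CLUE comfort, 8 CLUE vision, 8 MRD) on unadjusted 95% intervals for an odds ratio, and 5 preference questions on unadjusted 95% intervals for a preference ratio.
- **Tertiary gate.** The start of 14.7 allows testing only when all primary and secondary hypotheses are met. The lettered rules in 2.3, repeated in 14.4 and later in 14.7, open CLUE comfort and CLDEQ-8 items on partial success. Section 2.2 uses an and/or condition on the primary and secondary endpoints.

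**The concern.** Section 2.1 says the study is run mainly to support market claims, so the rule that turns data into a formal claim has to be unambiguous. For 12 items (8 CLUE comfort, 4 CLDEQ-8) it is not: which passage is followed decides whether there is any formal test. If that is settled after the data are seen, the choice can follow the results.

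The second issue is the breadth of the 5% sentence. A serial gate on one primary controls the primary. It does not control a family of tests that open together behind it, each at full level. Section 14.4 provides for only one of the two CLDEQ-8 secondaries being met, so the secondaries are not an all-must-pass set.

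**Working it through.** **1. The tertiary gate, side by side.**

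| Outcome | Start of 14.7 | Rules in 2.3, 14.4, later 14.7 | Section 2.2 |
|---|---|---|---|
| Primary met, no secondary met | No items | 8 CLUE comfort items, between arms | CLUE comfort items and CLDEQ-8 items |
| Primary met; of the secondaries, only within-arm CLDEQ-8 met | No items | 8 CLUE comfort and 4 CLDEQ-8 items, between arms | CLUE comfort items and CLDEQ-8 items |
| All met | All items, both comparisons | Same | Same |

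In the second row, rule 2d opens between-arm CLDEQ-8 items although the between-arm CLDEQ-8 hypothesis is the one that failed. Rule 2c is also garbled: it limits testing to the between-arm comparison and then adds the within-arm one. The word only looks stray.

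**2. The plan's own level.** I used a Satterthwaite t-test at one-sided 2.5%, SDs 25.21 and 18.12, and distance = effect + margin 5. Effects 3, 5 and 9 give 120, 77 and 40 per arm, matching Table 9. Power at 40 per arm is 80.3%. So each test works at one-sided 2.5%, and the primary and sample size stand.

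**3. Correlation of the two CLDEQ-8 secondaries.** Both use ARM 2's Visit 2 habitual scores. Section 14.2 gives an SD of 7.17 for ARM 1, and for ARM 2 "while a standard deviation of 5.0 was utilized for ARM2 in each calculation for the various effect sizes". I take 7.17 for ARM 2's AO1D change from baseline as well. For an assumed within-ARM-2 SD w of AO1D minus habitual:

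- covariance = 25 - (7.17² + 25 - w²)/2, which is 12.5 at w = 7.17;
- correlation = 12.5 / √((7.17² + 25) × 7.17²) = 0.20;
- for w from 4 to 9 it runs from -0.15 to 0.35.

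**4. Chance of at least one false secondary claim.**

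- *Both CLDEQ-8 nulls true, gate open.* If independent, 1 - 0.975² = 4.94%. At correlation 0.20 it is 4.84%. Over -0.15 to 0.35 it is 4.98% to 4.7%.
- *The same, with the gate opening at the planned 80%.* If the primary is independent of the secondaries, 0.80 × 4.84% = 3.87%. Over the correlations above and an assumed CLUE/CLDEQ-8 correlation q of 0 to 0.8, it is 3.8% to 4.6%.
- *All three nulls true, gate open.* If independent, 1 - 0.975³ = 7.31%. With 0.20 between the CLDEQ-8 tests and q = 0, 0.5, 0.7, 0.8 and 0.95, it is 7.2%, 6.8%, 6.4%, 6.2% and 5.5%.

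**5. Primary superiority branch.** With 40 per arm, a true CLUE difference of 0 and the between-arm CLDEQ-8 null true, the chance of a false primary superiority or first-secondary claim is 2.9% to 3.7% for q from 0 to 0.8.

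**6. Rule 2d.** Four between-arm items are tested after their total has failed. With the total at its null boundary, an assumed item correlation of 0.7 and item-total correlation of 0.75 to 0.85, the chance of at least one false item claim given that failure is about 4.8% to 4.3%.

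**The case against.** **The rate may never exceed 5%.** This largely stands. In the plausible case, two CLDEQ-8 nulls, the error stays below a literal 5%. The three-null case needs the gate open, which at 80% rests on a CLUE effect of +9, while the within-arm CLUE effect is -5 or worse: a reversal of at least 14 points on the same contrast. If the CLUE effect were at its null in both comparisons, the gate would open only about 2.5% of the time. A reader might infer that the plan breaches 5%. The documents support only that control at 5% is not guaranteed. The 2.5% benchmark is itself an inference from the two-sided 0.05 in section 14.2.

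**The tertiary items are exploratory.** Section 14.7 places them under that label and in support of the main endpoints. If so, the sentence in 14.4 covering all planned analysis is too broad, and narrowing it is enough.

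**The lettered rules sit under a heading that already assumes success.** In 2.3 and 14.7 rules a to d are nested under the case where the primary and secondary hypotheses are met. But rules b and d describe cases where some are not met, so nesting does not remove the conflict.

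**An adjustment may exist elsewhere.** Section 14.1 defers detail to a stand-alone SAP that was not supplied, and section 22 lists a Bonferroni reference that no visible text cites. The uncited reference proves nothing either way. The SAP could add an adjustment, but the protocol's conflicting gates would remain.

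**Tempting overstatements.** A reader might infer that each secondary is a free-standing marketing claim. The plan does not say this: its partial-success text governs which items open. A reader might also apply an unconditional four-test error rate to rule 2d. That ignores that the items are components of the total that has just failed.

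**Conclusion.** Two points hold.

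1. The tertiary gate contradicts itself for 12 items, rule 2d links between-arm items to the wrong hypothesis in one case, and one clause is garbled. This needs no modelling. Confidence is high.
2. The 5% statement covers more than the stated strategy controls. For the secondaries, control is not guaranteed: in the plausible case the error lies above 2.5% but not above a literal 5%, and it passes 5% only in the unlikely three-null case. For the 28 items and 5 preference questions, no control is provided. Confidence is moderate, because the SAP is not available and the sidedness of the 5% is not stated.

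The error figures rest on normal approximations, one-sided 2.5% tests, the Table 9 SDs, and assumed values for the within-ARM-2 SD and the correlations between instruments. The primary non-inferiority test and the sample size are not affected. This should be fixed before the data are seen.

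**What to change.** - **One tertiary gate.** State a single rule and align 2.2, 2.3, 14.4 and both parts of 14.7 to it. If partial opening is kept, tie between-arm CLDEQ-8 items to the between-arm CLDEQ-8 hypothesis and correct the garbled clause.
- **Scope of the 5%.** In 14.4, limit it to the hypotheses actually controlled and say it is two-sided (2.5% per direction). Label the tertiary items and secondary superiority tests supportive.
- **Secondaries.** If they are to be covered, name a procedure: a fixed sequence in the section 2.3 order, or Holm. Otherwise limit the 5% to the primary.
- **Primary superiority.** Say whether it is inside the controlled family (placed in the sequence or sharing alpha) or outside it and supportive. Left at full level beside a secondary sequence, it would keep the same kind of gap.

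The cost is wording plus some lost claims. With SDs 7.17 and 5.0, margin 3 and 40 per arm, power for the first secondary is 57% at a true difference of 0, and 99.0%, 99.9% and 99.99% at -3, -4 and -5. A fixed sequence would therefore block the later two in about 43% of trials at 0 (1 - 0.572), but in about 1% or fewer at -3 or better. Holm avoids that dependence but starts at 0.025/3 = 0.0083 one-sided. At that level the same test has 39% power at 0 and 99.5% at -4.

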### **14.5. Primary Analysis**

The primary endpoint is the change in CLUE comfort score from baseline to 2-week follow-up. The data from the ARM 1 (Test) will be compared to the first period of the ARM 2 (Control, habitual lens). The primary analyses will be conducted on the Per-Protocol (PP) population. A sensitivity analysis will be conducted on the Intent-to-Treat (ITT) population. Non-inferiority will be assessed on PP population, while superiority will be assessed on ITT population.

#### **Change in CLUE Scores:**

The CLUE comfort scores will be analyzed using a linear mixed model to assess the difference between the Test and Control (subjects' habitual lens) lenses. The regression model will include ARM (ARM1 – Test, and ARM 2 – Habitual Lens), time (Baseline and Follow-up evaluation) and ARM by time interaction as fixed effect factors. Baseline characteristics such as age and gender may be included as fixed effect covariates in the model when appropriate. Investigational site will be included as a random effect (G-side). An Unstructured (UN) or compound symmetric (CS) covariance or heterogenous compound symmetry (CSH) structures

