**Clinical Study Protocol**  
**Johnson & Johnson Vision Care, Inc.**

| ARM 2  |                                |  |
|---|--------------------------------|--|
| Visit 2: Treatment 1, 2-Week Follow-Up; Treatment 2 Fitting |                                |  |
| Step  | Procedure                      | Details  |
| 2.5.  | CLDEQ-8 Questionnaire          | 
The subject will respond to the CLDEQ-8 Questionnaire (Appendix A).
 
NOTE: If subjects no longer meet score criteria of <math>\geq 15</math>, the lenses will be removed by the subject and discarded. The subject will be discontinued and proceed to final evaluation (F.1)
   |
| 2.6.  | Follow Up questionnaires       | 
The subject will respond to the CLUE and MRD Follow Up Questionnaire (Appendix A)
   |
| 2.7.  | Entrance Visual Acuity         | 
Record the distance Snellen visual acuity with the contact lenses (OD, OS) to the nearest letter. Subjects must read the smallest line until at least 50% of the letters are read incorrectly.
  |
| 2.8.  | Subjective Lens Fit Assessment | 
Evaluate overall lens fit acceptance (acceptable or unacceptable) based on centration, movement and other fitting characteristics.
 
An unacceptable fit is deemed by one of the following criteria:
 
 
• limbal exposure at primary gaze or with extreme eye movement.
 
• edge lift.
 
• excessive movement in primary and up gaze.
 
• insufficient movement in all three of the following conditions: primary gaze, up gaze, and Josephson push up.
 
 
NOTE: if lens fit is unacceptable subject will be discontinued from the study.
 |
| 2.9.  | Lens Removal and Discard       | 
The lenses will be removed by the subject and discarded.
  |

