# **Clinical Study Protocol**

## **Johnson & Johnson Vision Care, Inc.**

- Subject not successfully dispensed due to lack of efficacy and safety including poor vision, poor comfort or unacceptable fit.

For discontinued subjects, the Investigator will:

- Complete the current visit (scheduled or unscheduled).
- Complete the Final Evaluation, indicating the reason that the subject was discontinued from the study.
- Record the spherocylindrical refraction with best corrected distance visual acuity.
- Collect used test article(s) (worn or brought to the visit) from the subject and discard them, unless otherwise stated in Section 7.2.
- Collect all unused test article(s) from the subject.
- Make arrangements for subject care, if needed, due to their study participation

An additional subject will be enrolled if a subject discontinues from the study prematurely.

In cases where a subject is lost to follow-up, every possible effort must be made to contact the subject and determine the reason for discontinuation/withdrawal. The measures taken to follow up must be documented including two written attempts and a certified letter (or equivalent) as the final attempt

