#### **Per-Protocol Population:**

All subjects who successfully complete all visits and do not substantially deviate from the protocol as determined by the trial cohort review committee prior to database hard lock. Justification for the exclusion of subjects with protocol deviations from the per-protocol population set will be documented in a memo to file.

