# Clinical Study Protocol

## Johnson & Johnson Vision Care, Inc.

### **CLUE Scores:**

The CLUE comfort scores will be analyzed using a linear mixed model to assess the difference between the Test (AO1D) and Control (subjects' habitual lens). The regression model will include lens type and baseline score as fixed effect factors. Baseline characteristics such as age and gender may also be included as fixed effect covariates in the model when appropriate. Investigational site will be included as a random effect. The correlation measurements from the same subjects across lens type will be modeled using UN variance-covariance matrix. If the estimation algorithm does not converge, then a CS or CSH covariance matrix will be used. The Kenward and Roger method will be used to calculate the denominator degree of freedom.

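### The primary between-arm model leaves out the baseline score; adjusting for it would narrow the CI by about 19% at the plan's SDs (8% to 26% over plausible correlations), provided the between-arm analysis set runs through Visit 2

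*Combined protocol and SAP*

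**What the plan says.** **Model.** Section 14.5 fits a linear mixed model to the CLUE comfort scores with ARM, "time (Baseline and Follow-up evaluation) and ARM by time interaction as fixed effect factors". Δ is the between-arm difference in mean change to Visit 2, tested against -5. Section 14.6 uses the same structure for the change in CLDEQ-8, with margin 3. Age and gender are named as optional covariates; the baseline score is not. The two within-ARM 2 models in 14.6 do adjust for it. For CLUE: "The regression model will include lens type and baseline score as fixed effect factors".

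**Analysis set.** Section 14.5: "The primary analyses will be conducted on the Per-Protocol (PP) population". Section 14.3 defines that set as "All subjects who successfully complete all visits and do not substantially deviate from the protocol". For ARM 2 this includes Visit 3. In section 7.2, step 2.5 of ARM 2 Visit 2 says of a subject whose CLDEQ-8 is no longer at least 15: "The subject will be discontinued and proceed to final evaluation (F.1". The CLUE questionnaire comes afterwards, at step 2.6. Section 8.2, by contrast, tells the investigator what to do for any discontinued subject: "Complete the current visit (scheduled or unscheduled".

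**Size.** Section 14.2: "All Sample size calculations were performed with 80% power and 2-sided alpha=0.05". The ARM 1 change SD is 25.21, and "a standard deviation of 18.12 was utilized for ARM2 in the calculation for each scenario". In Table 8, 18.12 is the SD of the habitual baseline score.

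**The concern.** When baseline is an outcome row with a free mean in each arm, the mixed model uses none of the information that baseline carries about follow-up beyond simple subtraction. Subtraction is the best use of baseline only when the regression slope of follow-up on baseline is 1. Table 8 implies a slope far below 1 on the Test lens, so subtracting baseline adds noise. The plan adjusts for baseline within ARM 2 but not in the randomised comparison, where the adjustment would tighten the test that gates every other hypothesis. The target of 40 per arm reaches 80% power only at the largest effect in Table 9; at +5 the same table needs 77 per arm.

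The gain cannot simply be taken under the analysis set as written. Exclusion of ARM 2 subjects with a low Visit 2 CLDEQ-8 depends on a post-randomisation outcome, affects one arm only, and removes controls who improved. It favours the Test lens under either model, and more so under the adjusted one.

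**Working it through.** **1. Reproduce Table 9.** Satterthwaite t-test, two-sided 0.05, SDs 25.21 and 18.12, distance = effect + 5. Required per arm for effects 3 / 5 / 9: 120 / 77 / 40 (power 80.2%, 80.1%, 80.3%), matching the table. Totals are 2n × 1.4 = 336 / 216 / 112.

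**2. Confirm that the planned model does not adjust.** On simulated complete data (40 per arm, unstructured covariance), a generalised least squares fit of ARM, time and ARM by time gave 9.708 (SE 5.303), identical to the difference in mean change. The choice of covariance structure does not alter this.

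**3. Correlations.**
- ARM 1, Table 8 overall: r = (18.78² + 18.12² - 25.21²)/(2 × 18.78 × 18.12) = 0.067. Fisher 95% CI with n = 24: -0.35 to 0.46.
- By study: 0.22 (n = 11), -0.59 (n = 5), 0.49 (n = 8). Without the five-subject study, about 0.31.
- ARM 2: the documents give no habitual-to-habitual correlation. If the score SD is 18.12 at both visits, a change SD of 18.12 implies r = 1 - 18.12²/(2 × 18.12²) = 0.5. This is an assumption.

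**4. Standard errors, CLUE, 40 per arm.**
- Unadjusted: √((25.21² + 18.12²)/40) = 4.91.
- Covariances: 0.067 × 18.12 × 18.78 ≈ 22.7 (ARM 1) and 0.5 × 18.12² ≈ 164.2 (ARM 2). Common slope = (22.7 + 164.2)/(2 × 18.12²) = 0.285.
- Residual SDs: 19.14 (ARM 1) and 16.17 (ARM 2). Adjusted SE = √((19.14² + 16.17²)/40) = 3.96, or 3.99 allowing for chance baseline imbalance.
- Variance ratio = 25.06²/31.05² = 0.65; CI narrower by 1 - √0.65 ≈ 19%.
- Power (non-central t, df 78 and 77): at +9, 80% to 93%; at +5, 52% to 70%.

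A simulation of 4,000 trials under these inputs agrees. The SD of the estimate falls by 19.2%. The mean CI half-width falls by 18.8% with model-based standard errors and by 17.1% with heteroscedasticity-robust ones.

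**5. Sensitivity.** Score SDs held, ARM 1 r from 0.067 to 0.46, ARM 2 r from 0.07 to 0.9: variance ratio 0.54 to 0.85, so the CI is 26% to 8% narrower. At r = 0.31 and 0.7, power at +9 goes from 92% to 97%.

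**6. CLDEQ-8 change.** ARM 1 r = (6.35² + 4.39² - 7.17²)/(2 × 6.35 × 4.39) = 0.147. ARM 2 r = 1 - 5.00²/(2 × 4.39²) = 0.351, assuming equal SDs at both visits. SE 1.38 unadjusted and 1.19 adjusted; variance ratio 0.74, CI 14% narrower. The range of the ratio is 0.67 to 0.97.

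**7. Analysis set.** Simulation with a true difference of -5 in the randomised population, Table 7 and 8 means and SDs, stable habitual scores, and 40 per arm analysed. There were 24 scenarios of 10,000 runs: ARM 1 r 0.067 or 0.31; ARM 2 r 0.5 or 0.7; CLUE–CLDEQ-8 correlation -0.4, -0.6 or -0.8; baseline CLDEQ-8 truncated at 15 or not. These settings are assumptions. Nominal one-sided error is 2.5%.

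| Analysis set | Change score | Baseline-adjusted |
|---|---|---|
| All Visit 2 data kept | 2.2% to 2.8% | 2.2% to 2.9% |
| ARM 2 below 15 excluded (7% to 11% of ARM 2) | 3.0% to 5.8% | 3.9% to 10.3% |
| Mean estimate under exclusion (truth -5) | -4.5 to -3.3 | -4.3 to -2.3 |

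The adjusted analysis suffers more for a simple reason. Exclusion lowers both the follow-up and the baseline CLUE means of the retained controls. A change score credits the whole baseline shift against the follow-up shift; the adjusted model credits only the slope times that shift.

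**The case against.** The planned model is not an error. It estimates exactly the Δ that 14.5 defines, against the margin and with the sample size built for it. At the historical mean difference of 14.72, power is already about 98% at the plan's SDs. The 19% depends on an ARM 2 correlation that the documents do not supply; holding ARM 2's change SD at 18.12 and varying its follow-up SD from 15 to 22 moves the gain from 24.5% to 13.0%. Cells with little gain are those where unadjusted power is already high. For CLDEQ-8 the gain could be as small as 1.5% (ratio 0.97). Adjustment alone, under the present Per-Protocol set, makes the error rate worse. An ITT sensitivity analysis is also planned.

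Most of this stands as qualification: the gain is uncertain, this is an efficiency point about a valid model, and the model change must not be made on its own. It does not remove the point. The CI narrowed in every correlation setting examined, and precision helps most if the true effect is nearer 5 than 14.72, which the discordant historical differences (16.9, -2.8, 22.6) leave open. The ITT analysis keeps discontinued subjects only if their Visit 2 CLUE score was recorded, and it does not repair the non-inferiority test, which 14.5 places on the Per-Protocol set.

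**Conclusion.** The point holds. The randomised comparison makes no use of the baseline score as a covariate, although the score is collected before randomisation and the plan uses it in the within-ARM 2 models. The best single estimate is a CI about 19% narrower for the primary endpoint, resting on ARM 1 r = 0.067 (24 subjects) and an assumed ARM 2 r = 0.5, with a range of 8% to 26%. For the CLDEQ-8 change it is about 14%. The gain is legitimate only if ARM 2 subjects discontinued at Visit 2 stay in the between-arm comparison; with all Visit 2 data kept, the error rate stays near 2.5%. The size of the inflation under exclusion depends on the simulation assumptions; its direction favours the Test lens. The change should be made, with medium confidence in its exact size.

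**What to change.** 1. In 14.5, and for the first secondary endpoint in 14.6, analyse the Visit 2 score (or the change) with ARM and baseline score as fixed effects and site as random. Keep the margins of -5 and 3 and the 95% CI rule. Let the residual variance differ by arm where the check already planned in 14.5 calls for it. Do not add the baseline score as a covariate while it remains an outcome row; an alternative is to keep the repeated-measures model and constrain the baseline means to be equal across arms.
2. For these two comparisons, define the analysis set on data through Visit 2, so that ARM 2 subjects discontinued there for CLDEQ-8 below 15 are not excluded for lacking Visit 3.
3. Reconcile step 2.5 in section 7.2 with section 8.2, so that it is clear the Visit 2 CLUE score is recorded for these subjects. The discontinuation rule itself is not addressed here.

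Item 1 should not be adopted without item 2.

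**Cost.** Wording only: the model and the analysis set in section 14 and in the stand-alone SAP that 14.1 says will be finalised before database lock, plus one procedural clarification. Because the model and set are protocol text, the change goes through a protocol revision. There is no new visit or assessment: baseline CLDEQ-8 and CLUE are taken at steps 1.6 and 1.8, before randomisation at step 1.16.
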